### 1.5. ME-401

Zandelisib (ME-401) is an orally bioavailable PI3K $\delta$  inhibitor with optimal pharmacologic properties, including high potency with half-maximal inhibitory concentration (IC50) for PI3K $\delta$  of 0.6 nM in a cellular assay, plasma half-life ( $t_{1/2}$ ) of approximately 28 hours supporting once-daily dosing, high volume of distribution indicating wide access to tissues, high specificity to the  $\delta$  isoform at clinically relevant concentrations, and prolonged residence time on the target.

ME-401 has demonstrated substantial single-agent anti-tumor activity in a Phase 1b dose-escalation study in patients with relapsed FL, small lymphocytic lymphoma (SLL), and chronic lymphocytic leukemia (CLL), with an ORR of 90% (Soumerai 2018) and manageable toxicity; 4 subjects with relapsed/refractory MZL treated on the intermittent schedule (IS) showed a 100% ORR (25% CR). These encouraging preliminary results justify the evaluation of ME-401 in a larger cohort of patients with FL and MZL.

[figure not shown]

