## 1.6. Experience with ME-401

### 1.6.1. Single Ascending Dose Healthy Volunteer Study

A single ascending dose study of zandelisib across a range of dose levels from 10 to 150 mg was conducted in normal healthy volunteers. Both maximum plasma concentration ( $C_{max}$ ) and area under the concentration versus time curve from time zero to the last timepoint ( $AUC_{[0 \text{ last}]}$ ) demonstrated linear increases over the dose range of 10 to 150 mg, with a time to maximum plasma concentration ( $t_{max}$ ) of 5–6 hours.

To assess the on-target pharmacodynamic (PD) effect of ME-401, inhibition of PI3K signaling in peripheral blood basophils was measured using a PD assay (basophil activation test [BAT]), which measured basophil activation by CD63 upregulation following ex-vivo stimulation with an anti-FC $\epsilon$ R1 monoclonal antibody. From the fitted maximum possible effect ( $E_{max}$ ) model, the concentrations of ME-401 estimated to give 50% and 90% BAT inhibition (i.e.,  $EC_{50}$  and  $EC_{90}$ , respectively) of the maximum effect ( $E_{max}$  91.6%) were 0.6 ng/ml and 5.2 ng/mL, respectively (Figure 2). Further pharmacokinetic (PK) modeling projected that a daily ME-401 dose of 60 mg will result in steady-state minimum plasma concentration ( $C_{min}$ ) in excess of 5 ng/mL, the  $EC_{90}$  in the BAT assay. This led to the selection of 60 mg as the initial dose level in the Phase 1b dose escalation study in subjects with indolent B-cell malignancies, a dose lower than the starting dose for oncology trials calculated based on animal toxicokinetic studies.

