### 1.6.2.3. Continuous and Intermittent Dosing Schedules

Initially, the Phase 1b study explored the CS of ME-401 dosing when the product was given daily continuously. To address the potential for delayed AEs, the protocol was amended to include a modified dosing schedule strategy with an intermittent schedule (IS) of ME-401 administered once daily for 7 days followed by 21 days without therapy in each 28-day cycle. Intermittent therapy was introduced after an initial 2 cycles of daily dosing. The rationale for these treatment-free intervals was to potentially enable reconstitution of T regulatory cells (TREGs). The kinetics of TREGs repopulation following the administration of TREG-specific cytotoxic therapy has been studied by others and, in general, numeric recovery of the CD4+/CD25+/FoxP3+ cell population requires approximately 2 weeks (Mahnke 2007). This suggested that a 3-week treatment break might be reasonable, allowing approximately 1 week for ME-401 wash-out (approximately 5 half-lives) and 2 weeks for functional TREGs recovery.

Overall, 46 of 47 subjects (97.9%) on CS dosing (including subjects with no switch to IS dosing or switched later than Cycle 3) had at least one TEAE; 22 (46.8%) experienced a Grade 3 TEAE and 3 (6.4%) experienced a Grade 4 TEAE. The most common TEAEs in  $\geq 25\%$  of subjects were diarrhea (19 [40.4%] subjects), cough (15 [31.9%] subjects), and fatigue (13 [27.7%] subjects). All other TEAEs on CS dosing occurred in  $< 25\%$  of subjects.

On CS dosing, median follow up was 210 days (range: 28–869, IQR: 99–627). Of the 47 subjects, 21 (44.7%) have discontinued therapy: 4 due to an AE, 9 due to disease progression, 1 due to the Investigator's decision, 4 due to the subject withdrawing consent, and 3 for stem cell transplantation.

All subjects who had completed at least 2 cycles of treatment at the time Amendment 6 was implemented were planned to switch to IS dosing. Overall, 39 of 43 subjects (90.7%) in the IS dosing group had at least one TEAE; 11 (25.6%) experienced a Grade 3 TEAE and 2 (4.7%) experienced a Grade 4 TEAE. The most common TEAEs were diarrhea (18 [41.9%] subjects), fatigue and nausea (12 [27.9%] subjects, each), and AST increased (9 [20.9%] subjects).

On the IS, median follow up was 155 days (range: 16–552, IQR: 57–308). Of the 43 subjects, 13 (30.2%) have discontinued therapy: 2 due to AE, 9 due to disease progression, 1 due to the subject withdrawing consent, and 1 for stem cell transplantation.

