## 5. STUDY DESIGN

### 5.1. Overall Study Design

This is a global, multicenter, open-label, single-arm, Phase 2 study of the PI3K $\delta$  inhibitor ME-401 in subjects with relapsed/refractory FL or MZL. ME-401 will be administered orally

at a dose of 60 mg given once a day. A cycle of treatment is 28 days in duration. Treatment with ME-401 is administered based on an intermittent schedule (IS).

The IS includes:

- continuous daily therapy for the initial 2 cycles of treatment
- the intermittent treatment begins at Cycle 3, with ME-401 administered daily for the first 7 days of every 28-day cycle (7 days on treatment and 21 days off treatment)

The first day of treatment is designated as Day 1. ME-401 will be administered until progressive disease (PD), development of unacceptable toxicity (despite ME-401 modified dosing schedule), or subject withdrawal.

Review of the ongoing Phase 1b study evaluating different dosing schedules for ME-401 in subjects with relapsed/refractory FL showed improved risk-benefit profile of the IS over a continuous schedule (CS, i.e., ME-401 given daily continuously). With Amendment 2, the initial CS treatment arm was terminated, and subjects were enrolled to receive therapy on the IS only. If subjects already completed 2 initial cycles of therapy, they were switched to IS dosing once they completed therapy in the ongoing cycle of treatment, and if they had not yet completed the first 2 cycles of therapy they were switched to IS dosing after completion of the first two cycles of therapy. Subjects who progress on IS dosing may be switched to CS dosing.

Upon confirmation of meeting eligibility criteria, subjects are enrolled and should be treated with ME-401 within a reasonable time frame (within 5 days). It is important to ensure that subjects continue meeting protocol specified eligibility criteria to enroll in the study, and if there are >7 days between screening laboratory assessments and expected Cycle 1 Day 1 dosing, then the laboratory assessments should be repeated and reviewed prior to the first dose of ME-401.

The study schema is presented in [Figure 1](#).

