## 9.6. Cardiac Evaluation

12-lead ECGs will be performed at the following visits:

- Screening

- Pre-dose on Cycle 1 Day 1 (unless the Screening visit is within 3 days prior to Day 1)
- Pre-dose on Day 1 of Cycles 3, 6, 13, 19, and 25
- On Day 1 of Cycles 1 and 3 at the expected time of  $C_{max}$  (3–5 hours after dosing)
- After Cycle 25, every 6 months, pre-dose
- EOT/30-Day Safety Follow-up visit
- As clinically indicated

Left ventricular ejection fraction measurement by echocardiogram or MUGA will be performed at screening, EOT/30-Day Safety Follow-up visit, and as clinically indicated.

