- k. **Hepatitis B and C testing** – Hepatitis B core antibody, Hepatitis B surface antigen, and hepatitis C antibody are required. Hepatitis B PCR is required if hepatitis B core antibody and/or surface antigen is positive. Hepatitis C PCR is required if hepatitis C antibody is positive.
- l. **Adverse events** – Recorded from the time of the first dose of study drug on Cycle 1 Day 1 and continues until 30 days after the last dose of study drug or start of new anti-cancer treatment.
- m. **Concomitant medications** – Recorded from 28 days prior to Cycle 1 Day 1 until the EOT/30-Day Safety Follow-up visit, or start of new anti-cancer treatment. Please, record information about COVID-19 vaccination, if performed.
- n. **ECG** – 12-lead ECGs performed at screening; Cycle 1 Day 1 pre-dose (unless the Screening visit is within 3 days prior to Day 1); pre-dose on Day 1 of Cycles 3, 6, 13, 19, and 25, and every 6 months thereafter; at the EOT/30-Day Safety Follow-up visit, and as clinically indicated. ECGs should be performed pre-dose. For Cycle 1 Day 1 and Cycle 3 Day 1, ECGs should be taken pre-dose and at expected Cmax (3–5 hours after dosing).
- o. **CBC with differential** – WBC, ANC, RBC, HGB, HcT, lymphocytes, eosinophils, monocytes, basophils, platelets, and MCH. Screening labs must be repeated if performed >7 days prior to Cycle 1 Day 1.
- p. **Serum chemistry** – Glucose, BUN or urea, creatinine, sodium, potassium, chloride, calcium, ALP, AST, ALT, total bilirubin, total protein, albumin, LDH, and phosphorous. Screening labs must be repeated if performed >7 days prior to Cycle 1 Day 1.
- q. **Coagulation** – aPTT, PT/INR. Screening labs must be repeated if performed >7 days prior to Cycle 1 Day 1.

- r. **Urinalysis** – Dipstick or urine test (pH, specific gravity, glucose, ketones, blood, and protein). Screening labs must be repeated if performed >7 days prior to Cycle 1 Day 1.
- s. **COVID-19 test results** – Please record COVID-19 test results in the AE CRF page, if positive.
- t. **Issue and Assess Compliance Diary** – Compliance diary to record daily study drug administration. Returned diaries are to be assessed for study product compliance. New compliance diary is to be issued with each dispensing of ME-401.

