#### **8.6. Cardiac Evaluations**

12-lead ECGs parameters including hear rate, RR interval, PR interval, QRS interval and QTcF will be assessed. For each parameter, the observed values and change from baseline will be summarized by visit.

The overall ECGs interpretations will be collected as ‘Normal’, ‘Abnormal, not clinically significant’ and ‘Abnormal, clinically significant. Shift tables from baseline will be produced based on these categories for each post-baseline. In addition, the incidence rate of grade 3 and above QT prolongation will be summarized by visit.

All 12-lead ECG data will be listed. In addition, the results of echocardiogram will be listed.

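### For subjects who stay on the intermittent schedule, no scheduled ECG after Cycle 3 Day 1 is taken with drug on board, yet SAP 8.6 tabulates QTcF by visit without separating on-drug from washed-out readings

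*Protocol*

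**What the plan says.** **Dosing.** Protocol Section 5.1 gives "continuous daily therapy for the initial 2 cycles of treatment" and, from Cycle 3, "7 days on treatment and 21 days off treatment" in each 28-day cycle. Subjects who progress on the IS may switch to continuous dosing (CS).

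**ECGs.** Section 9.6 sets ECGs at screening, before the first dose, "Pre-dose on Day 1 of Cycles 3, 6, 13, 19, and 25", pre-dose every six months after Cycle 25, at the end-of-treatment (EOT) visit 30 (±3) days after the last dose, and as clinically indicated. Only Cycle 1 Day 1 and Cycle 3 Day 1 also have a post-dose ECG. Footnote n of Appendix 1 says of those two days that "ECGs should be taken pre-dose and at expected C max (3–5 hours after dosing").

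**Pharmacokinetics.** Section 1.5 gives a half-life "of approximately 28 hours supporting once-daily dosing". Section 1.6.2.3 plans the treatment break as "allowing approximately 1 week for ME-401 wash-out (approximately 5 half-lives") plus two weeks of cell recovery. Section 1.6.1 reports that, after single doses in healthy volunteers, exposure "demonstrated linear increases over the dose range of 10 to 150 mg, with a time to maximum plasma concentration" of 5 to 6 hours.

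**Analysis.** SAP Section 8.6 summarises observed ECG values and change from baseline by visit, and adds that "the incidence rate of grade 3 and above QT prolongation will be summarized by visit". SAP Section 5.4 uses nominal visits without re-assignment. SAP Section 5.1 leaves unscheduled assessments out of summary tables unless stated otherwise, and splits safety tables by actual dose schedule.

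**The concern.** The ECG days suit continuous dosing, where a Day 1 pre-dose reading is a 24-hour trough. On the IS the same visit comes at the end of the drug-free interval. By-visit rows from Cycle 6 on would then show little drug effect by construction, and could be taken for long-term on-treatment cardiac data.

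Section 5.5 allows QT-prolonging drugs with caution throughout. If one is started after Cycle 3 Day 1, no scheduled ECG shows the combination on a dosing day. The same nominal visit can also mean different things: washed out in a subject still on the IS, a 24-hour trough in one switched to CS. SAP 5.1 does not say in which column ECGs taken after such a switch appear.

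**Working it through.** Half-lives elapsed = hours since last dose / 28. Residual fraction = 2^(−half-lives elapsed).

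1. **The protocol's own wash-out figure.** 5 × 28 h = 140 h = 5.8 days; 168 h / 28 h = 6.0 half-lives. About one week for about five half-lives is reproduced.

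2. **Pre-dose Day 1 of Cycles 6, 13, 19 and 25 on the IS.** The last dose is on Day 7 of the previous cycle and the next on Day 29 of that count, a gap of 22 days. 22 × 24 / 28 = 528 / 28 = 18.9 half-lives; residual about 0.0002%.

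3. **Visit window of ±7 days (Appendix 1, footnote a), with dosing tied to the visit.** The gap is 15 to 29 days: 360 / 28 = 12.9 to 696 / 28 = 24.9 half-lives. The largest residual is 0.013%.

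4. **EOT ECG.** 27 to 33 days: 648 / 28 = 23.1 to 792 / 28 = 28.3 half-lives.

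5. **Sensitivity to the half-life (assumed 24 to 36 h).** 528 / 24 = 22.0 and 528 / 36 = 14.7. At the early window edge with 36 h, 360 / 36 = 10.0. The conclusion does not change.

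6. **What is observed on drug.** Cycle 1 Day 1 post-dose, Cycle 3 Day 1 pre-dose and Cycle 3 Day 1 post-dose. The Cycle 3 readings follow 56 daily doses when dosing was uninterrupted. The pre-dose one is 24 / 28 = 0.86 half-lives after the last dose. A later seven-day course reaches 1 − 2^(−7 × 24/28) = 1 − 2^(−6) = 98.4% of steady state, so no later IS week exceeds the exposure on Cycle 3 Day 1.

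7. **Where a later on-drug reading could be had.** Cycle 6 Day 7 is already a pharmacokinetic visit. Pre-dose that day, six doses have been taken: 1 − 2^(−6 × 24/28) = 97% of the steady-state trough.

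8. **ECG at 3–5 h against tmax of 5–6 h.** The two ranges meet only at 5 h. The size depends on a model not in the documents: one compartment, first-order absorption, half-life 28 h, absorption rate set to give a single-dose tmax of 5, 5.5 or 6 h, and no lag. The 3-hour level is then 89–94% of Cmax on Cycle 1 Day 1. By Cycle 3 Day 1 accumulation moves the modelled tmax to 3.8–4.4 h, and the level at 3 to 5 h is 98–100% of Cmax. An assumed absorption lag of up to 2 h widens the 3-hour figures to 66–94% (first dose) and 89–99% (steady state).

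**The case against.** **A reader might infer that on-drug QTc is barely observed.** The documents do not support that. Three on-drug ECGs are scheduled, two of them normally at steady state and one at about the highest exposure of the regimen. What stands is that none is repeated later.

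**The Cmax timing.** A reader might take the 3–5 h label as a serious miss. The 5–6 h figure comes from single doses in healthy volunteers, no steady-state tmax is given, and the modelled loss at Cycle 3 is small. It is an inconsistency to tidy up.

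**Concentration and QTc.** The only time shared by a scheduled ECG and a pharmacokinetic sample is before the first dose, so a reader might infer that no concentration–QTc relation can be derived. That goes too far. Sampling is sparse by design, population PK and exposure-response work has its own plan, and model-predicted concentrations at ECG times could be used.

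**The SAP does not call these visits on-drug.** True. The risk is in how an unlabelled table is read, and a label removes it.

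**Mitigations exist.** Entry limits on QTcF, a caution on QT-prolonging drugs and ECGs as clinically indicated all help. QT prolongation is not among the adverse events of special interest. But SAP 5.1 drops unscheduled ECGs from the tables by default, so an on-drug reading obtained that way would appear only in a listing.

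**Enrollment is closed** (Section 8.3). This stands, and it rules out any change to Cycle 1 Day 1 procedures.

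**Conclusion.** The point holds in this form: for subjects who stay on the IS, four of the five listed pre-dose Day 1 ECGs, and the EOT ECG at its planned time, are taken after complete plasma wash-out, at least 12.9 half-lives after the last dose. Late on-drug QTc is therefore not observed on schedule. The rows of SAP 8.6 from Cycle 6 on describe washed-out IS subjects, possibly mixed with CS troughs.

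This rests on the 28-hour half-life holding in patients and on dosing as planned. Three limits apply:

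- The six-monthly ECGs after Cycle 25 follow the same pattern if taken on Day 1 of a cycle, as Section 8.5 implies. Section 9.6 names no day, and the window there is ±1 month.
- Appendix 1 lets the EOT visit come earlier when urgent new treatment is needed, so some EOT ECGs may be on drug.
- Subjects who interrupted dosing in Cycles 1–2 may not be at steady state on Cycle 3 Day 1.

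All three favour classifying by actual time rather than by visit. This is a worthwhile, inexpensive correction to a safety table; it does not touch the primary analysis and is not evidence of a QT effect.

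**What to change.** **(a) SAP Section 8.6, the main change.** Classify every ECG, unscheduled ones included, by actual time since last dose from the recorded dosing dates. Base on-treatment QTcF change and Grade 3 or higher QT incidence on ECGs within 140 h (5 half-lives) of the last dose. Report the others separately as off-drug. Use no blanket label by cycle, so that subjects switched to CS are classified correctly. Cost: a little extra programming, and few on-drug readings after Cycle 3, which the table should make visible. It works on data already collected, provided dosing dates are recorded by interval, as the exposure calculations in SAP 8.1 already require.

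**(b) Protocol Section 9.6 and Appendix 1.** For any subject not yet past Cycle 6, take the Cycle 6 ECG at the existing Day 7 pharmacokinetic visit instead of pre-dose on Day 1. No visit or ECG is added. With enrollment closed, this may reach few or no subjects.

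**(c) Wording, minor.** Reconcile the 3–5 h expected-Cmax label in Section 9.6 and Appendix 1 footnote n with the 5–6 h tmax in Section 1.6.1, or state the basis for the difference.

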## 9.7. Laboratory Tests

Laboratory tests listed on the Schedule of Assessments ([Appendix 1](#)) will be analyzed at the investigative site's local laboratory and used in all safety analyses and response assessments (see [Appendix 5](#)); PK samples discussed in [Section 7.4](#) will be shipped to a central laboratory for analysis.

The following tests are to be performed:

- CBC with differential: white blood cell (WBC), ANC, red blood cell (RBC), hemoglobin (HGB), hematocrit (HcT), lymphocytes, eosinophils, monocytes, basophils, platelets, mean corpuscular hemoglobin (MCH)
- Serum chemistry: glucose, blood urea nitrogen (BUN) or urea, creatinine, sodium, potassium, chloride, calcium, alkaline phosphatase (ALP), AST, ALT, total bilirubin, total protein, albumin, LDH, phosphorus
- Coagulation: activated partial thromboplastin time (aPTT), prothrombin time (PT)/international normalized ratio (INR)
- Urinalysis: Dipstick or urine test (pH, specific gravity, glucose, ketones, blood, protein)
- Pharmacokinetic sampling (see [Section 7.4](#))
- Pregnancy test
- HIV testing
- Hepatitis B and Hepatitis C testing
- PCR test for CMV
- OI monitoring:
  - CD4 (for subjects with signs of infection)
  - Blood cultures if febrile neutropenia occurs, or when ANC is NCI CTCAE Grade 4
  - PCR for CMV (every cycle for first 6 months of treatment and every 3 months thereafter). If PCR test is positive for CMV, treatment should be delayed until recovery. Treatment of CMV should be initiated based on local SOC. Retreatment

with ME-401 will be allowed without dose reduction once PCR test for CMV is negative.

Subjects with identified risk factors will have the following tests performed:

- CD4 and CD8 count and ratio, c-reactive protein, blood cultures
- Any additional laboratory and diagnostic methods according to local SOC reported as unscheduled laboratory and diagnostic methods of assessment
- Radiological imaging (i.e., chest X-ray or CT scans)

Note: Treatment of the OI that started while on study should be based on local SOC.

- Bone marrow aspiration/biopsy: performed at screening at the discretion of the Investigator and repeated as indicated for subjects with known or suspected marrow involvement. Bone marrow aspiration/biopsy is to include surgical pathology, immunohistochemistry, and flow cytometry as per SOC. Bone marrow aspiration/biopsy is required to confirm a CR when a nodal CR is documented by a CT scan.
- There is no requirement for routine COVID-19 testing. However, if a patient is found to have a positive COVID-19 test, enter the COVID-19 results in the AE CRF page. Also, enter any AEs associated with COVID-19 infection in the AE CRF page.

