**Table 4: ME-401 Toxicity Management (Continued)**

Toxicity	Grade*	Management of ME-401	Management of Toxicity
	≥3	
 
Permanently discontinue ME-401.
 
	
 
Treat per institutional standard of care, including systemic corticosteroids.
 

Lung Infection/ Pneumonia	2	
 
Holding ME-401 is not required. Continue ME-401.
 
Dosing may continue at 60 mg administered on the IS.
 
	
 
Treat per institutional standard of care.
 

	3	
 
Hold ME-401 until AE resolved to Grade ≤1 or baseline.
 
Resume ME-401 at 60 mg administered on the IS.
 
Discontinue if same event occurs a third time.
 
	
 
Treat per institutional standard of care.
 

	4	
 
Permanently discontinue ME-401.
 
	
 
Treat per institutional standard of care.
 

Cytomegalovirus (CMV)	Any	
 
If test is positive (PCR or antigen assessment) based on local laboratory assessments and requires treatment, then hold ME-401 until recovery.
 
Resume ME-401 on the IS after resolution of asymptomatic CMV reactivation if all the following conditions are met: 
 
CMV reactivation is resolved per the Investigator assessment
 
 
 
CMV reactivation was not associated with end organ disease (e.g., pneumonia, hepatitis, gastroenteritis, retinitis, encephalitis).
 
	
 
Treat per institutional standard of care.
 
If all conditions for restarting study drug are met, then secondary CMV prophylaxis must be maintained as per institutional guidelines.
 

Hematological Toxicity	3	
 
Grade 3 neutropenia, febrile neutropenia or thrombocytopenia: ME-401 dosing may continue.
 
	
 
Perform CBC weekly until resolves to Grade ≤2 (unless myelosuppression is due to follicular lymphoma).
 

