## 5.4. Monitoring and Prophylaxis of Opportunistic Infection

### 5.4.1. Monitoring for Opportunistic Infection

In addition to the clinical review and laboratory tests outlined in the Schedule of Assessments ([Appendix 1](#)), the following should be performed in all subjects prior to start of every cycle of treatment with ME-401:

- Evaluation of any new onset or worsening of pulmonary symptoms (i.e., cough, dyspnea, or fever) that includes a lung examination at each visit prior to treatment to rule out opportunistic infection (OI), including PJP *Pneumocystis jirovecii* pneumonia/PCP (*pneumocystis* pneumonia).
- Laboratory tests:
  - CD4 (for subjects with signs of infection)
  - Blood cultures if febrile neutropenia occurs, or when ANC by NCI CTCAE is Grade 4
  - PCR for CMV (every cycle for first 6 months of treatment and every 3 months thereafter). If PCR test is positive for CMV and treatment is initiated, then treatment with ME-401 should be delayed until recovery. Treatment of CMV should be initiated based on local SOC. Retreatment with ME-401 will be allowed on the IS once PCR test for CMV is negative. Please note: quantitative results from PCR measurements must be reported for all CMV assessments.

Implement enhanced monitoring prior to start of every cycle of treatment with ME-401 when prior medical history or laboratory parameters could be associated with one of the following risk factors:

- Intensive chemotherapy ( $\geq 2$  lines of myelosuppressive cytotoxic therapy)

- History of symptomatic CMV infection, systemic herpes
- History of lower respiratory tract infection
- History of immunodeficiency in the last 12 months (excluding lymphoma)
- Lymphocyte count  $<500/\text{mm}^3$  while on treatment in clinical study

For subjects with identified risk factors and those who developed an OI while on study treatment, additional assessments may include:

- CD4 and CD8 count and ratio, c-reactive protein, blood cultures
- Any additional laboratory and diagnostic methods according to local SOC reported as unscheduled laboratory and diagnostic methods of assessment
- Radiological imaging (i.e., chest X-ray or CT scans)
  - Note: Treatment of the OI that started while on study should be based on local SOC.

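### The protocol's three CMV rules disagree on when to hold ME-401 and on who may restart it

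*Protocol*

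**What the plan says.** The protocol gives CMV dosing instructions in three places.

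**When to hold ME-401**
- Table 4, CMV row: "If test is positive (PCR or antigen assessment) based on local laboratory assessments and requires treatment, then hold ME-401 until recovery".
- Section 5.4.1: "If PCR test is positive for CMV and treatment is initiated, then treatment with ME-401 should be delayed until recovery".
- Section 9.7: "If PCR test is positive for CMV, treatment should be delayed until recovery". This sentence does not name the drug, but the later sentence on retreatment shows that ME-401 is meant.

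**When to restart**
- Table 4: "Resume ME-401 on the IS after resolution of asymptomatic CMV reactivation if all the following conditions are met". The conditions are that the Investigator judges the reactivation resolved, and that "CMV reactivation was not associated with end organ disease". It adds: "If all conditions for restarting study drug are met, then secondary CMV prophylaxis must be maintained as per institutional guidelines". It does not name a negative PCR.
- Section 5.4.1: "Retreatment with ME-401 will be allowed on the IS once PCR test for CMV is negative".
- Section 9.7: retreatment "will be allowed without dose reduction once PCR test for CMV is negative".

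Neither 5.4.1 nor 9.7 refers the reader to Table 4 for CMV. Neither mentions end-organ disease or secondary prophylaxis in connection with restart.

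**The concern.** A site that receives a positive CMV result needs one answer to two questions: does the drug stop, and when may it start again? The three places give different answers.

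On restart, the risk is re-exposure. Table 4 excludes subjects who had CMV end-organ disease and requires secondary prophylaxis for those who do restart. The other two sections let a negative PCR open the way to restart without either safeguard.

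On the hold, the risk is lost therapy. Section 9.7 stops the drug for a positive PCR that nobody intends to treat and allows it back only when PCR is negative. Section 5.3.1 requires permanent discontinuation after more than 6 continuous weeks of interruption unless the Medical Monitor authorizes a restart. A subject whom Table 4 would never have held could therefore come off treatment.

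The matter is the safety and dosing of subjects still on drug. It has no bearing on the ORR hypothesis, alpha or sample size.

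**Working it through.** There is no plan figure to reproduce. The check applies each rule as written to the situations a site can meet.

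| Situation | Table 4 | Section 5.4.1 | Section 9.7 |
|---|---|---|---|
| A. Positive PCR, CMV treatment neither needed nor started | No hold | No hold | Hold |
| B. CMV with end-organ disease, now PCR-negative | Restart conditions not met | Restart allowed | Restart allowed |
| C. Symptomatic CMV without end-organ disease, now PCR-negative | No provision for restart | Restart allowed | Restart allowed |
| D. Treated asymptomatic reactivation, resolved and PCR-negative | Restart with mandatory secondary prophylaxis | Restart; prophylaxis not mentioned | Restart; prophylaxis not mentioned |
| E. Asymptomatic reactivation judged resolved, PCR still positive | Restart not excluded | Not allowed | Not allowed |

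Reading across:

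1. **Hold (A).** Section 9.7 is the outlier. Table 4 and 5.4.1 differ only in saying that treatment is required or that it has been started.
2. **Restart (B, C).** Sections 5.4.1 and 9.7 permit what Table 4 does not provide for. B is a direct conflict on a safety limit.
3. **Prophylaxis (D).** Sections 5.4.1 and 9.7 omit the requirement; they do not contradict it.
4. **Resolution standard (E).** Table 4 relies on the Investigator's judgement, the other two on PCR. E arises only if an Investigator calls a PCR-positive reactivation resolved, which Table 4 neither states nor rules out.
5. **Schedule at restart.** There is no conflict. Section 9.7 is silent on schedule, and Section 5.3.1 resumes interrupted treatment on the IS.

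**Exposure to the conflict**
- Scheduled CMV PCRs after first dose, from the CMV row of Appendix 1: Day 1 of Cycles 2, 3, 4, 5, 6, 7, 10, 13, 16 and 19, which are study days 29, 57, 85, 113, 141, 169, 253, 337, 421 and 505. That is 6 + 4 = 10 tests by the 18-month point (day 547). The next, at Cycle 22, falls on day 589.
- Subjects treated on the IS, from Section 8.3: 121 FL + 32 MZL = 153.
- Time still to run: MZL enrollment closed on 31 August 2022 (Section 5.1). Planned dosing is about 18 months (synopsis, Study Duration), so an MZL subject enrolled at closure would be dosing until about the end of February 2024. The reference list in this version cites a source accessed on 11 October 2022, so the text was current while late enrollees could still be on drug.

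These figures count testing opportunities and people at risk. They do not count cases in which the rules diverge.

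**The case against.** The strongest reply is that Table 4 already governs. Section 5.3 sends dose interruption and discontinuation to Section 5.3.1, and prevention and management of opportunistic infection to Section 5.4. Section 5.3.1 says toxicities on the IS are managed by Table 4, and Section 8.5 points to Table 4 for dosing changes after adverse events. On that reading, 5.4.1 covers monitoring and 9.7 is only a list of tests. The restart sentences are also permissive: they say restart is allowed and do not say a negative PCR is sufficient, so a careful site could satisfy all three by applying every condition together.

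Part of this stands. The general direction is toward Table 4, and the rules can be combined. But no precedence is stated, and 5.4.1 and 9.7 contain their own CMV-specific dosing sentences at the place where the test is ordered. A site acting on a result there could reasonably follow them.

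Other safeguards are partial:
- Section 5.4.2 says prophylaxis should be started when the risk factors in 5.4.1 are present. The CMV factor listed there is past symptomatic infection. Asymptomatic reactivation, the only case in which Table 4 provides for restart, is not listed, and the wording is weaker than Table 4's obligation.
- Other Table 4 rows require permanent discontinuation for Grade 4 colitis, hepatotoxicity, lung infection and other related events. A first Grade 2 or Grade 3 lung infection does not end treatment under its row.
- Medical Monitor authorization for restart is required only after more than 6 weeks off drug. Earlier consultation is recommended, and it concerns interruption and discontinuation rather than restart.

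On the hold trigger, 9.7 next mentions starting CMV treatment, so it may be a shortened form of 5.4.1 and errs toward caution. That explains the wording but does not remove the different answer in situation A.

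**Conclusion.** The concern holds on both points. Section 9.7 stands alone in delaying ME-401 on any positive PCR. Sections 5.4.1 and 9.7 allow restart on a negative PCR without Table 4's end-organ limit or its mandatory secondary prophylaxis. The end-organ limit is the serious part, because a subject whom Table 4 would not re-dose may be re-dosed under the other two. The prophylaxis point is an omission, and the hold point is an inconsistency in the cautious direction.

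The reach is at most those of the 153 IS subjects still on drug, each with up to 10 scheduled CMV tests after first dose in 18 months. The documents state neither the number still dosing nor a CMV positivity rate, so the number of affected cases is unknown. The conclusion assumes only that a site may act on 5.4.1 or 9.7 as written, since nothing there sends it to Table 4. It should be fixed, but it does not threaten the trial's efficacy conclusions.

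**What to change.** Make the CMV row of Table 4 the only CMV dosing rule, and state it as follows:

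- **Hold** ME-401 if PCR or antigen is positive and CMV treatment is required or has been started.
- **Restart** at 60 mg on the IS only if the reactivation was asymptomatic, is resolved in the Investigator's judgement with a negative PCR, and involved no end-organ disease. Maintain secondary CMV prophylaxis according to local institutional guidance.

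Replace the hold and restart sentences in Sections 5.4.1 and 9.7 with a cross-reference to that row.

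The negative PCR is not in Table 4 today, but 5.4.1 and 9.7 already require it, so the merged restart rule joins existing conditions and adds no new one. If the sponsor prefers Investigator judgement alone, that can be defended, but the protocol should then say so in one place only.

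The cost is a protocol wording change or a clarification letter to sites with subjects still on drug. No new data or assessments are needed.
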